We have included placebo control conditions for each study drug, to assist with interpretation of the study results. Since this study will recruit healthy individuals and we will not be removing access to a known treatment, we believe that inclusion of the placebo conditions poses low risk to participants.

- f. Definition of treatment failure or participant removal criteria.

Participants will be removed from the study if they remove their consent to participate, become pregnant, refuse to adhere to the study session schedule, or if it becomes clear that their continued participation could put them at increased risk (e.g., develop a chronic pain condition that requires treatment, onset of a medical/psychiatric disorder). These decisions will be made in conjunction with the BPRU medical team.

- g. Description of what happens to participants receiving therapy when study ends or if a participant's participation in the study ends prematurely.

N/A

5. Inclusion/Exclusion Criteria

Inclusion Criteria:

- Aged 18-75
- Urine sample tests negative for common illicit substances of abuse, including cannabis
- Medically cleared to take study medications

- Are not pregnant or breast feeding
- Willing to comply with the study protocol.

Exclusion Criteria:

- Meet DSM-5 criteria for alcohol/substance use disorder
- Taking opioids for pain
- Previous adverse reaction to a cannabinoid product
- Prescribed and taking stimulants or benzodiazepines
- Answer “yes” to item 1 of the Brief Pain Inventory indicating chronic pain
- Self-report any illicit drug use in the past 7 days
- Presence of any clinically significant medical/psychiatric illness judged by the investigators to put subject at elevated risk for experiencing an adverse event
- History of seizure disorder
- Have a known allergy to the study medications or sesame seed oil
- Taking medications contraindicated with hydromorphone or dronabinol
- Have a history of clinically significant cardiac arrhythmias or vasopastic disease
- Have an abnormal and clinically-significant ECG
- Failure to discriminate between hydromorphone and placebo in the Screening 2/Qualifying session.

6. Drugs/ Substances/ Devices

- a. The rationale for choosing the drug and dose or for choosing the device to be used.

Study Drugs: Hydromorphone and dronabinol will be over-encapsulated by our research pharmacy and administered orally.

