a. Hydromorphone: Administration of any drug involves some risk because it is not always possible to predict individual response to drugs. The most likely risk in this study is that subjects will experience side-effects of the drugs that may be unpleasant. Common side effects of hydromorphone are light-headedness, dizziness, sedation, nausea, vomiting, sweating, flushing, dysphoria, euphoria, dry mouth, and pruritus. Less frequently observed side effects are weakness, headache, agitation, tremor, uncoordinated muscle movements, alterations of mood (nervousness, apprehension, depression, floating feelings, dreams), muscle rigidity, paresthesia, muscle tremor, blurred vision, nystagmus, diplopia and miosis, transient hallucinations and disorientation, visual disturbances, insomnia, increased intracranial pressure, flushing of the face, chills, tachycardia, bradycardia, palpitation, faintness, syncope, hypotension, hypertension, bronchospasm and laryngospasm, constipation, biliary tract spasm, ileus, anorexia, diarrhea, cramps, taste alteration, urinary retention or hesitancy, antidiuretic effects, urticaria, other skin rashes and diaphoresis. Side effects of hydromorphone are generally temporary, dissipate within several hours, and are dose-dependent. Thus, participants may only experience side-effects occasionally during the research study. Serious potential adverse effects of hydromorphone administration that are possible but extremely unlikely to be encountered in this study are respiratory depression and loss of consciousness. The FDA has identified the following conditions as increasing the risk for respiratory depression or other serious side effects following hydromorphone administration: patients with status asthmaticus; chronic obstructive pulmonary disease; reduced respiratory function; high blood pressure; impairment of hepatic, pulmonary or renal functions; myxedema or hyperthyroidism; adrenocortical insufficiency; gall bladder disease; acute alcoholism; history of convulsive disorders; history of head injury; currently taking sedatives, hypnotics or phenothiazines; and sulfite allergy. Mean exposure to hydromorphone is also increased 4-fold among patients with hepatic impairment and 3-fold among patients with renal impairment. Therefore, to further reduce the risk serious side effects, we will exclude any potential participant who exhibits one or more of these conditions.

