The most serious potential adverse event following hydromorphone administration is opioid agonist overdose, which is characterized by respiratory depression, somnolence progressing to stupor or coma, skeletal muscle flaccidity, cold and clammy skin, constricted pupils, and sometimes bradycardia and hypotension. In serious overdosage, particularly following intravenous injection, apnea, circulatory collapse, cardiac arrest and death may occur. We believe the risk of overdose in this study to be low for the following reasons: we have extensive experience in the administration of hydromorphone, we have chosen doses that have been demonstrated to be safe and tolerable in an identical participant population, we will exclude any individual who has a medical condition that

may increase the risk for respiratory depression and/or other adverse events, all medication doses will be administered by a trained research nurse, and participants will be monitored throughout the study session, up to 8 hours, by trained staff who will have access to the opioid antagonist naloxone to reverse the opioid agonist effects. Hydromorphone has no known interactions with dronabinol.

b. Dronabinol: The FDA identifies the following adverse effects of dronabinol: cardiovascular (hypertension, hypotension, palpitations, tacharrhythmia, vasodilation); dermatologic (flushing); gastrointestinal (abdominal pain, nausea, vomiting, xerostomia); neurological (amnesia, ataxia, confusion, coordination problem, dizziness, somnolence, vertigo), and psychiatric (anxiety, delusion of persecution, depersonalization, depression, disturbance in thinking, euphoria, hallucinations), though it should be noted that the adverse effects were collected from studies of patients undergoing chemo therapy or with advanced HIV, which may have decreased their threshold for experiencing negative effects. Dronabinol is listed as pregnancy category C, meaning that preclinical studies have revealed adverse effects on the fetus but that no controlled human studies have been conducted to assess this risk (pregnancy or breast-feeding will be an exclusion criterion). The only absolute contraindication of dronabinol is allergy or hypersensitivity to cannabinoids or sesame oil. Dronabinol has moderate – severe interactions with breast cancer resistance protein inhibitors (topotecan, ataluren), and has moderate interactions with the antiretroviral protease inhibitor ritonavir (Norvar), which is used to treat HIV and AIDS.

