a. Protection Against Hydromorphone Risks: We have extensive experience in the administration of hydromorphone and other opioid agonists in controlled laboratory settings and therefore anticipate few problems. Any individual who may be prone to the risks associated with hydromorphone will be excluded from participating. Although research staff and participants will be blinded to the exact medication provided, both groups will be informed of the potential side effects and risks associated with the study drug administration. Participants will be free to discontinue study participation at any time without consequence. The dose of hydromorphone that is being administered is consistent with clinical care, and is a medium level dose for the treatment of pain. Further, The Qualifying Session provides us a unique opportunity to assess for sensitivity to hydromorphone, and any participant who shows intolerance to hydromorphone during the Qualifying Session will be excluded from the primary study. Great care has been taken in selecting the appropriate drug doses to ensure hydromorphone is well-tolerated and safe for our participants and participants will also be able to discontinue study participation at any time. The most serious risk associated with hydromorphone administration is respiratory depression. We believe this risk is minimal in this study for several reasons. First, we are administering a mid-level dose and have extensive experience administering

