b. Protection Against Dronabinol Risks: The majority of risks that are known to occur following dronabinol administration are psychiatric in nature. These risks are recognized as being transient and readily reversible. To mitigate these risks, we will exclude participants who endorse having previously experienced negative effects to cannabinoid products. We will also conduct psychiatric screening during the Screening session to ensure that patients with current or history of psychiatric events are excluded from study participation. Further, all participants will be informed about the potential side effects of the study medications and will be permitted to end study participation at any time if they experience negative events, with no consequences. Finally, we are providing participants with taxi service to and from the study sessions to ensure no persistent drug effects will impact their driving. We are also budgeting for the potential for a participant to stay the night at the CRU following study drug exposure. Based on our previous experience, we expect this to be a rare occurrence but are prepared to make that option available as needed.

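### Section 8 excludes everyone with any of 13 listed hydromorphone risk conditions, or any current or past psychiatric event, but Section 5 leaves most of these to clinical judgement, so the protocol holds two different eligibility rules.

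*Combined protocol and SAP*

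**What the plan says.** **Section 8a (Medical risks), Hydromorphone.** The protocol lists conditions that it says raise the risk of respiratory depression or other serious side effects. They include "patients with status asthmaticus; chronic obstructive pulmonary disease; reduced respiratory function; high blood pressure; impairment of hepatic, pulmonary or renal functions" and "myxedema or hyperthyroidism; adrenocortical insufficiency; gall bladder disease; acute alcoholism; history of convulsive disorders; history of head injury", followed by current use of sedating drug classes and sulfite allergy. It adds: "Mean exposure to hydromorphone is also increased 4-fold among patients with hepatic impairment and 3-fold among patients with renal impairment". It then commits: "we will exclude any potential participant who exhibits one or more of these conditions". In the overdose paragraph that follows, one of the reasons for calling the risk low is that "we will exclude any individual who has a medical condition that" may raise the risk of respiratory depression or other adverse events.

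**Section 8b (Steps taken to minimize the risks).** For hydromorphone: "Any individual who may be prone to the risks associated with hydromorphone will be excluded from participating". For dronabinol, psychiatric screening is to "ensure that patients with current or history of psychiatric events are excluded from study participation".

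**Section 5 (Inclusion/Exclusion Criteria).** The general medical exclusion is: "Presence of any clinically significant medical/psychiatric illness judged by the investigators to put subject at elevated risk for experiencing an adverse event". Medical clearance for the study drugs is an inclusion criterion. Named exclusions include alcohol or substance use disorder, seizure disorder, prescribed stimulants or benzodiazepines, medications contraindicated with either study drug, allergy to the study drugs or sesame oil, significant arrhythmia or vasospastic disease, and a clinically significant abnormal ECG. The age range is 18 to 75.

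**Section 7d (Early stopping rules).** The largest potential risk is said to be cardiovascular. Part of the answer is that participants are healthy and not predisposed to raised blood pressure or heart rate.

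**The concern.** The Section 8a list is unconditional: having a listed condition is enough to exclude. The Section 5 catch-all applies only if three things hold: the illness is present, it is clinically significant, and the investigators judge that it raises risk. These are different rules, and they can give different answers for the same volunteer.

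What is at stake is whether the enrolled population is the one that the risk statements describe. A body that approves the study on the strength of Section 8 would take these conditions to be excluded outright. Staff who apply the Section 5 criteria as written could accept some of the same people.

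**Working it through.** No arithmetic is involved beyond a count, and the plan gives no figure to reproduce. The check sets the Section 8 statements beside Section 5.

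**1. The Section 8a list.** Split at its semicolons, it has 13 entries.

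| Section 8a entry | Route in Section 5 |
|---|---|
| Convulsive disorders | Named (seizure disorder) |
| Acute alcoholism | Named (DSM-5 alcohol use disorder) |
| Sedatives, hypnotics, phenothiazines | Partly named (benzodiazepines); the contraindicated-medication criterion may reach others |
| Sulfite allergy | Not named; the study-drug-allergy criterion may reach it |
| Status asthmaticus | Clearance or catch-all only |
| COPD | Clearance or catch-all only |
| Reduced respiratory function | Clearance or catch-all only |
| High blood pressure | Clearance or catch-all only |
| Hepatic, pulmonary or renal impairment | Clearance or catch-all only |
| Myxedema or hyperthyroidism | Clearance or catch-all only |
| Adrenal insufficiency | Clearance or catch-all only |
| Gall bladder disease | Clearance or catch-all only |
| Head injury | Clearance or catch-all only |

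Count: 13 − 2 named − 1 partly named = 10 not named. Of those 10, one (sulfite allergy) has a possible specific route, which leaves 10 − 1 = 9 that depend wholly on medical clearance or the catch-all.

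**2. Psychiatric history.** Section 8b excludes current and past events. The Section 5 catch-all speaks of the presence of illness. A past, resolved event is barred by the first and need not be by the second.

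**3. Can someone meet one rule and fail the other?** Yes. Take a volunteer with controlled high blood pressure or an old head injury, medically cleared and judged not to be at raised risk. That person meets Section 5 on this point and is excluded by Section 8a.

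**4. Does screening close the gap?** The Screening Visit text in Section 4a provides an ECG, hepatic, hematologic and chemistry blood tests, and a history and physical. The eligibility measures include the MINI psychiatric interview. These would detect many of the conditions. But the text gives no eligibility thresholds, lists no respiratory function test, and does not refer to the Section 8a list. Detecting a condition does not say whether it excludes.

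**5. Which Section 8 statements are firm rules?** Two: the Section 8a list and the psychiatric sentence in Section 8b. The overdose paragraph and the hydromorphone paragraph of Section 8b speak of people who may be at raised risk and give no list of their own, so they too need medical judgement.

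**6. How far does the safety case depend on exclusion?** The overdose paragraph gives five reasons for low risk: experience with the drug, choice of dose, exclusion of risk-raising conditions, administration by a nurse, and monitoring with naloxone available. Exclusion is one of the five. Separately, the blood-pressure assumption in Section 7d has no matching named criterion in Section 5.

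**The case against.** The best defence is that the sections belong to one protocol and should be read together. Section 5 excludes illness judged to raise the risk of an adverse event. Section 8a can then be taken as the investigators' advance statement of which conditions they will judge that way. Screening supplies the means to find them before any dosing, and no document shows that staff would work from Section 5 alone.

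Part of this stands. Section 5 is not silent, and medical clearance could well remove most people with these conditions. But Section 5 never refers to the Section 8a list, and its test remains one of judgement. Reading the sections together also does not bring in a past psychiatric event, because the catch-all is limited to illness that is present.

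Four stronger readings are tempting, and the documents do not support them:

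- A reader might infer that people at raised risk will in fact be enrolled. The documents show only that the criteria as written permit it. Nothing shows that a person with hepatic or renal impairment would pass the blood tests and clearance, so the 4-fold and 3-fold exposure figures do not measure the effect of this defect.
- A reader might infer that the low-risk argument rests wholly on exclusion. It is one of five reasons, and Section 8b adds a tolerance check and respiratory monitoring standards.
- A reader might infer that 10 of 13 conditions are left uncovered. The count is of names. Several entries overlap (the respiratory ones in particular), and it says nothing about numbers of people.
- A reader might infer a loss of precision from exposure differing between participants. The design is within-subject, with the same 4 mg hydromorphone dose in the four active conditions, so stable differences between people largely cancel in the dronabinol comparisons. No statistical consequence is claimed.

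**Conclusion.** The concern holds as an inconsistency between two eligibility rules. Section 8a and the psychiatric sentence in Section 8b exclude outright, while Section 5 leaves most of the same conditions to judgement. Of the 13 entries, 2 are named in Section 5, 1 is partly named and 10 are not named.

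It is more than missing detail, because the two rules can give opposite answers for the same person on a point that the safety case partly relies on. It should be corrected. It is not evidence of harm, and it changes no sample size, power or analysis. The conclusion assumes only that the Section 5 criteria mean what they say and that no screening checklist outside these documents already carries the Section 8a list.

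**What to change.** The sponsor should reconcile Section 5, the Section 8a list and the psychiatric sentence in Section 8b so that one eligibility rule applies throughout, with one wording for psychiatric history. Either of two routes would do this: carry the Section 8 conditions into Section 5, or reword Section 8 to say that these conditions are matters of medical judgement. This review does not say which clinical rule is right.

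Whichever is adopted, the risk statements should then match it: the blood-pressure assumption in Section 7d, the overdose paragraph in Section 8a, and the hydromorphone paragraph in Section 8b.

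The cost is protocol and screening wording. If the Section 8 list is moved into Section 5, there may also be more screen failures. The documents give no basis for estimating how many, and with an age range up to 75 the number should not be assumed to be small.
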